10.1 Efficacy, Safety, and Pharmacokinetic Assessments

10.1.1 Efficacy Assessments

The efficacy assessments will be completed by the investigator or appropriately qualified study center staff. Every effort should be made to ensure that each instrument is completed by the same assessor at each visit.

10.1.1.1 Pediatric Anxiety Rating Scale

The PARS is a clinician-rated instrument for assessing the severity of anxiety symptoms associated with common anxiety disorders including GAD in children^{10,11}.

The PARS severity score for GAD will be assessed for all symptoms identified in the generalized anxiety section of the PARS symptom checklist and the scores recorded on the eCRF.

10.1.1.2 Clinical Global Impression of Severity

The CGI-S was developed for use in clinical trials to provide an assessment of the clinician's view of the patient's global functioning prior to and after initiating a study medication^{12,13}.

The CGI-S will be completed using a 7-point scale and the scores recorded on the eCRF.

10.1.1.3 Children's Global Assessment Scale

The CGAS can be used as a measure of global functioning and impairment¹⁴.

The CGAS will be completed by the clinician using a 100-point scale ranging from 1 to 100, with higher scores indicating better functioning. The scores will be recorded on the eCRF.

10.1.1.4 Global COVID-19 Impact Assessment

A global COVID-19 impact assessment will be used to evaluate the impact of the coronavirus disease pandemic on the severity of the subject's GAD during the last 1 week. The rating will include scores from 0 (not applicable, subject not enrolled in the trial during the pandemic) to 7 (extreme impact). Raters will also evaluate whether the impact was an improvement or worsening of the subject's GAD. The global COVID-19 impact assessment will be completed last after all study assessments by appropriately qualified study center staff and the scores recorded on the eCRF. Every effort should be made to ensure that the assessments are completed by the same assessor at each visit.

CONFIDENTIAL

10.1.2 Safety Assessments

10.1.2.1 Columbia-Suicide Severity Rating Scale

The C-SSRS is an instrument designed to systematically assess and track suicidal ideation and behavior¹⁵. The strength of this suicide classification system is in its ability to comprehensively identify suicidal events while limiting the over-identification of suicidal behavior.

The C-SSRS will be completed by the investigator or appropriately qualified study center staff and the scores recorded on the eCRF. Every effort should be made to ensure that the assessments are completed by the same assessor at each visit.

Any positive score should be reported to the medical director and immediate subject care should be implemented and documented. Any positive score should be recorded as an AE or SAE, as appropriate.

In addition to the planned assessments, the investigator must continually evaluate suicidality risk throughout the subject's participation in the study.

10.1.2.2 Adverse Events

Adverse Event Definition

An AE is defined as any untoward medical occurrence in a clinical study subject administered a medicinal product which does not necessarily have a causal relationship with this treatment. An AE can therefore be any unfavorable and unintended sign (including an abnormal laboratory finding), symptom, or disease temporally associated with the use of a medicinal (investigational) product, whether or not it is related to the medicinal (investigational) product. This includes an exacerbation of pre-existing conditions or events, intercurrent illnesses, drug interaction or the significant worsening of the indication under investigation that is not recorded elsewhere in the eCRF under specific efficacy assessments. Anticipated fluctuations of pre-existing conditions, including the disease under study that do not represent a clinically significant exacerbation or worsening need not be considered AEs.

It is the responsibility of the investigator to document all AEs that occur during the study. AEs will be elicited by asking the subject a nonleading question, for example, "Have you experienced any new or changed symptoms since we last asked/since your last visit?". AEs should be reported on the appropriate page of the eCRF.

CONFIDENTIAL

Assessment of Severity

Each AE will be assigned a category by the investigator as follows:

Mild: An AE that is easily tolerated by the subject, causes minimal discomfort and does not interfere with everyday activities.

Moderate: An AE that is sufficiently discomforting to interfere with normal everyday activities; intervention may be needed.

Severe: An AE that prevents normal everyday activities; treatment or other intervention usually needed.

If there is a change in severity of an AE, it must be recorded as a separate event.

Assessment of Causality

Every effort will be made by the investigator to assess the relationship of the AE, if any, to the study drug. Causality should be assessed using the categories presented in the following table:

Unrelated: Clinical event with an incompatible time relationship to study drug administration, and that could be explained by underlying disease or other drugs or chemicals or is incontrovertibly not related to the study drug.

Unlikely: Clinical event whose time relationship to study drug administration makes a causal connection improbable, but that could plausibly be explained by underlying disease or other drugs or chemicals.

Possible: Clinical event with a reasonable time relationship to study drug administration, but that could also be explained by concurrent disease or other drugs or chemicals.

Probable: Clinical event with a reasonable time relationship to study drug administration, and is unlikely to be attributed to concurrent disease or other drugs or chemicals.

Very Likely/Certain: Clinical event with plausible time relationship to study drug administration, and that cannot be explained by concurrent disease or other drugs or chemicals.

Action Taken

The investigator will describe the action taken in the appropriate section of the eCRF, as follows:

- None
- Study drug stopped

CONFIDENTIAL

- Study drug temporarily interrupted
- Concomitant medication
- Other, specify.

Follow-up of Adverse Events

All investigators should follow up subjects with AEs until the event is resolved or until, in the opinion of the investigator, the event is stabilized or determined to be chronic. Details of AE resolution must be documented in the eCRF.

Documentation and Reporting of Adverse Events

All AEs from the signing of the informed consent form (ICF) until 30 days after receiving the last dose of study drug will be collected according to the procedures outlined above at the timepoints specified in the Schedule of Assessments ([Section 8.1.2/8.1.3](#)), and as observed or reported spontaneously by study participants.

AEs should be reported and documented in accordance with the procedures outlined below. All AEs occurring during the study must be documented on the relevant eCRF pages. The following data should be documented for each AE:

- Description of the symptom event
- Classification of 'serious' or 'not serious'
- Severity
- Date of first occurrence and date of resolution (if applicable)
- Action taken
- Causal relationship
- Outcome of event (unknown, recovered, recovering, not yet recovered, recovered with sequelae, death [with date and cause reported]).

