^b If a site becomes aware of any adverse events after study completion (occurring outside of a defined study visit, including any contact up to 30 days after receiving the last dose of study drug), all adverse events reported by the patient or patient representative or observed or otherwise identified by the investigator or other study personnel must be documented.

^c Visit window \pm 3 days. Refer to [Section 8.2.2.1, Table 1](#) for visit windows for safety assessments (physical examination, BMI, vital signs, ECG, urine drug screen, clinical chemistry including thyroid, hematology, urinalysis, pregnancy test) and/or PK assessments missed due to remote visits.

^d Vital signs (blood pressure, pulse rate, temperature, and respiration rate) will be recorded at every visit. Height and weight will be recorded at Visit 1 (Screening), Visit 5 (Week 4), and Visit 7 (Week 8/ET) only.

^e Fasting blood sample.

^f A serum pregnancy test will be performed at Visit 1 (Screening); a urine pregnancy test will be performed at Visit 2 (Baseline) and Visit 7 (Week 8/ET) for females of childbearing potential.

^g To be completed last after all other study assessments.

^h Subjects who can tolerate the current dose of 10 mg/day may have a dose escalation to 20 mg/day at the investigator's discretion taking into account the CGI-S score.

ⁱ For PK blood sampling for assented/consented subjects at Visit 5 (Week 4) and Visit 7 (Week 8/ET), 2 blood samples per subject will be collected at each of these visits for escitalopram and S-demethylcitalopram analysis at the following times: Visit 5 (Week 4): for subjects receiving dose in the morning, at 0 h (predose) and \geq 1 h postdose and for subjects receiving dose in the evening, 2 samples at random times during the visit (ie, postdose from the dose received the previous evening), collected at least 2 hours apart from each other; and Visit 7 (Week 8/ET): 2 samples at random times during the visit (ie, postdose from the dose received in the morning or the previous evening), collected at least 2 hours apart from each other.

^j Subjects should take their first dose of study drug in clinic.

CONFIDENTIAL

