8.3.2 Inclusion Criteria

To be eligible for study entry subjects must satisfy all of the following criteria:

1. Subject's parent/legal representative must give written informed consent, including privacy authorization, prior to study participation. The subject will complete an informed assent prior to study participation.
2. Subject's parent/legal representative and the subject, if capable, are judged to be reliable by the investigator to keep all appointments for clinical visits, tests, and procedures required by the protocol.
3. Subject's parent/legal representative and the subject, if capable, must have a degree of understanding such that they can communicate intelligently with the investigator and study coordinator.
4. Subjects, male or female, must be between 7 and 17 years old, inclusive, at the time of consent/assent and at the Baseline Visit.
5. Subject meets DSM-5 criteria for a primary diagnosis of GAD at Screening established by a comprehensive psychiatric evaluation and confirmed/supported using the Mini-International Neuropsychiatric Interview for Children and Adolescents (MINI Kid).
6. Diagnosis of moderate or greater severity of GAD as determined by the following:
 - a. Presence of ≥ 4 symptoms identified on the generalized anxiety subsection of the Pediatric Anxiety Rating Scale (PARS) symptom checklist, 2 of which are “excessive worry” and “dread or fearful anticipation” (nonspecific) at the Screening and Baseline Visits.
 - b. PARS severity score of ≥ 15 at the Screening and Baseline Visits for symptoms identified on the generalized anxiety subsection of PARS symptom checklist, derived by summing 5 of the 7 severity/impairment/interference items (2, 3 5, 6, and 7).

CONFIDENTIAL

c. CGI-S rating of ≥ 4 at the Screening and Baseline Visits.

7. Male subjects who are sexually active with a partner of childbearing potential must use, with their partner, a condom plus an approved method of highly effective contraception from the time of informed consent until 14 days after the last dose of study drug. The following methods are acceptable:

- Combined (estrogen and progestogen containing) hormonal contraception associated with inhibition of ovulation:
 - oral
 - intravaginal
 - transdermal
- Progestogen-only hormonal contraception associated with inhibition of ovulation
 - oral
 - injectable
 - implantable intrauterine device
 - intrauterine hormone-releasing system
- Surgical sterilization (vasectomy or bilateral tubal occlusion)

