10.1.2.2.4 Warnings and Precautions

Clinical Worsening/Suicide Risk: subjects should be monitored for clinical worsening, suicidality and unusual change in behavior, especially at the start of therapy or at times of dose changes. (See [Section 10.1.2.1](#) for use of the C-SSRS).

Serotonin Syndrome: serotonin syndrome has been reported with SSRIs, including escitalopram, when taken alone, but especially when co-administered with other serotonergic agents (including triptans, tricyclic antidepressants, fentanyl, lithium, tramadol, tryptophan, buspirone, amphetamines, and St. John's Wort). Serotonin syndrome symptoms may include mental status changes (eg, agitation, hallucinations, delirium, and coma), autonomic instability (eg, tachycardia, labile blood pressure, dizziness, diaphoresis, flushing, and hyperthermia), neuromuscular symptoms (eg, tremor, rigidity, myoclonus, hyperreflexia, and incoordination) seizures, and/or gastrointestinal symptoms (eg, nausea, vomiting, and diarrhea). If symptoms of serotonin syndrome occur, escitalopram should be discontinued and supportive treatment initiated.

Hyponatremia: hyponatremia may occur as a result of treatment with SSRIs, including escitalopram. Subjects taking diuretics or who are otherwise volume depleted may be at greater risk. Discontinuation of escitalopram should be considered in subjects with symptomatic hyponatremia and appropriate medical intervention should be instituted.

Caution should be used when escitalopram is taken in combination with other centrally acting drugs.

Full details of the Warnings and Precautions associated with escitalopram are available in the prescribing information.

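### The only active adverse-event question is put to the child; no on-study passage tells staff to ask the parent as well

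*Protocol*

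**What the plan says.** Protocol Section 10.1.2.2 makes the investigator responsible for documenting every adverse event, then gives the method: "AEs will be elicited by asking the subject a nonleading question". The sample question that follows is worded to the child. Later in the same section, events are collected by those procedures at the scheduled timepoints "and as observed or reported spontaneously by study participants". Section 10.1.2.2.1 uses the same wording for serious events.

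The visit instructions (Sections 9.1.2 to 9.3.1) tell staff to record events since the last visit and name no informant. Section 9.4.1 describes the Week 10 call as a safety review, also without an informant. The remote schedule in 8.1.3 adds nothing on this point.

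A representative is named as a source in footnote b of the schedules (8.1.2 and 8.1.3), which covers events "reported by the patient or patient representative or observed or otherwise identified by the investigator". That footnote opens with "If a site becomes aware of any adverse events after study completion", so it addresses late reports and not scheduled visits.

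Three other provisions matter. On age: "Subjects, male or female, must be between 7 and 17 years old, inclusive, at the time of consent/assent and at the Baseline Visit". Inclusion criterion 3 reads in part: "Subject's parent/legal representative and the subject, if capable, must have a degree of understanding". Section 10.1.2.2.4 says "subjects should be monitored for clinical worsening, suicidality and unusual change in behavior", especially when treatment starts or the dose changes, and does not say who is to be asked.

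**The concern.** Safety is half of the primary objective, and the incidence of treatment-emergent adverse events is the first safety endpoint listed in Section 11.6. Some of the events to be watched for in this drug class, such as irritability, agitation, emotional lability and hypomania (all listed in Section 8.3.5 for discontinuation), are changes in behaviour that others may notice before the child does. A child of 7 or 8 may answer an open question about new symptoms truthfully and still not mention them. The parent is a natural second source, and the protocol already relies on the parent for reliability and communication (inclusion criteria 2 and 3).

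If the rule is followed as written, a parent's observation enters the data only when it is volunteered. Whether that happens may vary across the roughly 40 centers. Events missed equally in both arms lower the incidence in each and narrow the absolute difference between them.

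**Working it through.** The plan states no figure for this point, so there is none to reproduce. The check is of the text, followed by one illustration on assumed inputs.

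**Routes by which an event can enter the data**

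| Route | Source | Parent asked? | When |
|---|---|---|---|
| Open question | Protocol 10.1.2.2 | No, the subject | Scheduled contacts |
| Observation or spontaneous report | 10.1.2.2 | Not named | Any time, unsolicited |
| Positive C-SSRS score | 10.1.2.1 | Informant not stated | Screening to Week 9 |
| Physical examination | 10.1.2.5 | Not applicable | Screening and Week 8/ET |
| Abnormal laboratory finding | 10.1.2.2 (definition), 10.1.2.3 | Not applicable | Screening and Week 8/ET |
| Report by a representative | Footnote b, 8.1.2 and 8.1.3 | Accepted if it reaches the site | After study completion |

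Four things follow.

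1. Only the first row is an active, general search for events, and it is addressed to the child.
2. The C-SSRS covers suicidality and not other behavioural change. Physical examination and the laboratory tests fall at the two ends of the study. At Weeks 1 to 6, non-suicidal behavioural events depend on the child's answer, on what staff see, and on what someone volunteers.
3. Section 8.1 says that nearly all scheduled safety assessments other than the C-SSRS cannot be done remotely, and Section 17.3 allows ordinary telephone contact. On a telephone visit staff may not see the child, so the spoken question carries most of the weight.
4. Footnote b shows that the sponsor accepts a representative's report as valid. It names that source after completion, while the on-study text does not.

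**Illustration of what under-capture would do**

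Let p be the true incidence of an event in an arm and s the share captured. Neither is in the documents; both are assumptions. If s is the same in both arms:

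- observed incidence = s × p
- observed risk difference = s × (p1 − p0), which shrinks with s
- observed risk ratio = (s × p1)/(s × p0) = p1/p0, which does not change

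The common-event table (Section 11.6.1.1) lists events in at least 2% of subjects in any group. With the planned 128 per arm, 0.02 × 128 = 2.56, so 3 subjects are needed. The chance that one arm reaches 3 is P(X ≥ 3) with X ~ Binomial(128, s × p):

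| True rate p | s = 1.0 | s = 0.8 | s = 0.6 | s = 0.5 |
|---|---|---|---|---|
| 4% | 0.890 | 0.780 | 0.596 | 0.473 |
| 6% | 0.985 | 0.948 | 0.843 | 0.742 |
| 10% | 1.000 | 0.998 | 0.985 | 0.957 |

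Events near the 2% reporting line are sensitive to incomplete capture; common events are not. The table shows the direction and where it would be felt. It does not estimate what this trial would lose.

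**The case against.** The strongest reply is that the quoted sentence describes one prompt and not the whole of event collection. The investigator must document all events, no passage tells staff to disregard a parent, and the visit instructions do not limit the informant. Behaviour and suicidality must be monitored throughout. Inclusion criterion 3 ensures that the parent can communicate with the site. Staff may well question an accompanying parent as a matter of course, and site instructions outside these documents may say so.

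Much of this stands. It rules out reading the protocol as collecting events from the child alone, and silence about the parent is not proof that parents go unasked. It does not remove the gap: where the protocol specifies an active question, it specifies the child, and the other routes do not replace a question to the parent, least of all by telephone.

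A reader might also infer four stronger things that the documents do not support:

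- **That the entry criteria admit children who cannot communicate.** The phrase about capability in inclusion criteria 2 and 3 suggests it. But every subject must complete an assent, and exclusions 2 and 21 remove intellectual disability and English too limited for the assessments. The sound argument is narrower: young children may not report their own behavioural change.
- **That the loss can be put at some percentage.** Any such figure returns the capture rate that was assumed.
- **That the drug will look safer by every measure.** With equal capture the absolute difference shrinks, but the risk ratio does not.
- **That adverse-event rates in the two age strata become non-comparable.** Neither Section 11.6.1.1 nor SAP Section 10.1 plans an adverse-event table by age group, and randomization is stratified by age, so an age-related reporting loss should be balanced across arms.

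**Conclusion.** The point holds as a risk built into the elicitation rule. Parent-observable events, mainly behavioural ones in younger children and at telephone visits, may be under-ascertained because no on-study instruction has staff ask the parent. It is not a demonstrated bias, and its size cannot be estimated from these documents.

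The conclusion rests on two premises: that sites follow Section 10.1.2.2 as written, and that a parent sometimes notices a change that a child does not report. The first would fail if site instructions outside these documents already require the parent to be asked. The second is a judgement, though footnote b and the required behaviour monitoring are consistent with it. This is an inexpensive improvement to a primary-objective measurement and does not call the design into question.

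**What to change.** Amend Section 10.1.2.2 so that, at every visit (in clinic or remote) and at the Week 10 call, the same nonleading question is put to both the subject and the parent or legal representative. State that an event reported by both is recorded once. Extend footnote b in 8.1.2 and 8.1.3, or add a matching sentence in 10.1.2.2, so that a representative's report is a named source during the study as well as after it. Repeat the rule in the site instructions so that all centers apply it alike.

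The cost is a short protocol change and a note to sites, with no added visit. The downside is a few more minor events recorded in both arms. Because the question is asked identically in both arms under blinding, the comparison between them is preserved.

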10.1.2.2.1 Serious Adverse Events

Serious Adverse Event Definition

An SAE is any untoward medical occurrence or effect that, at any dose,

- Results in death.
- Is life-threatening (an AE is life-threatening if the subject was at immediate risk of death from the event as it occurred, ie, it does not include a reaction that might have caused death if it had occurred in a more serious form).
- Requires or prolongs inpatient hospitalization. (Complications occurring during hospitalization are AEs and are SAEs if they cause prolongation of the current hospitalization. Hospitalization for elective treatment of a pre-existing non-worsening condition is not, however, considered an AE. The details of such

CONFIDENTIAL

hospitalizations must be recorded on the medical history or physical examination page of the eCRF).

- Results in persistent or significant disability/incapacity. (An AE is incapacitating or disabling if it results in a substantial and/or permanent disruption of the subject's ability to carry out normal life functions).
- Results in a congenital anomaly/birth defect.

In addition, medical and scientific judgement is required to decide if prompt notification is required in situations other than those defined for SAEs above. This may include any event that the investigator regards as serious that did not strictly meet the criteria above but may have jeopardized the subject or required intervention to prevent one of the outcomes listed above, or that would suggest any significant hazard, contraindication, side effect, or precaution that may be associated with the use of the investigational product.

Reporting of Serious Adverse Events

Any SAEs from the signing of the ICF until 30 days after receiving the last dose of study drug will be collected according to the procedures outlined above at the timepoints specified in the Schedule of Assessments ([Section 8.1.2/8.1.3](#)), and as observed or reported spontaneously by study participants, whether or not the SAE is considered to be related to the investigational product.

The sponsor is required to inform worldwide regulatory authorities of SAEs that meet specific criteria. Therefore, the sponsor must be notified immediately regarding any SAE that occurs after informed consent is obtained.

Within 24 hours of learning of any AE that meets one of the criteria for an SAE, the study center personnel must report the event to Global Drug Safety on the SAE Form for Clinical Trials. The medical director may also be notified by telephone, however, notification of the medical director by telephone does not substitute for reporting of the event to the sponsor by email/fax of the SAE form for Clinical Trials within the required time period.

If, during follow-up, any nonserious AE worsens and eventually meets the criteria for an SAE, that AE should be recorded as a new SAE.

The study center must transmit the SAE Form for Clinical Trials to the SAE email address or fax number shown below. Even if an initial report is made by telephone, the SAE Form for Clinical Trials completed with all available details must still be faxed or emailed within 24 hours of knowledge of the event at the study center.

Supplemental information should be submitted as soon as available and may include laboratory results, radiology reports, progress notes, hospital admission and emergency

CONFIDENTIAL

room notes, holding and observation notes, discharge summaries, autopsy reports, and death certificates.

The investigator is expected to take all therapeutic measures necessary for resolution of the SAE. Any medications or procedures necessary for treatment of the SAE must be recorded on the appropriate pages of the subject's eCRF. All SAEs are to be followed by the study staff until resolution or until the SAE is deemed stable. *The sponsor may contact the study center to solicit additional information or follow up on the event.*

Fax or email the SAE Form for Clinical Trials to the following SAE fax number/email address:

[contact] (back-up [contact])
Email: [contact]

